c) The null hypothesis is accepted, but no statistically significant differences are observed between any of the treatments.

If the observed differences between all three agents are less than 15%, then the choice of initial treatment will likely be based on side effects, convenience, costs, etc.

Although this trial will not be able to definitively answer that issue, data collected from this study will allow planning of additional studies to address issues of cost-effectiveness, health-related quality of life, patient preferences, etc.

NICHD Reproductive Medicine Network
PPCOS-Pregnancy in Polycystic Ovary Syndrome Protocol
Given these considerations, at most two comparisons are needed

- Scenario 1: Point estimate of live birth rate with combination therapy higher than with either agent alone

Comparisons: (1) Combination therapy vs. highest single agent, (2) single agents to each other.

Rationale: In order to be preferred, combination therapy needs to be superior to both agents. If combination is not superior to the agent with the highest live birth rate, demonstration of superiority to the other agent is not clinically meaningful. Direct comparison of single agents becomes the critical comparison for decision making.

- Scenario 2: Combination therapy less effective than one of the single agents

Comparisons: 1

Rationale: Given cost, complexity, side effects, etc., combination therapy must be demonstrably more effective than single agent therapy in order to be clinically preferable. In this scenario, only the comparison between the two single agents is meaningful.

5. Sample Size Calculations

Primary Endpoint - Live Birth Rate

Assumptions

- 15% absolute difference considered to be clinically meaningful
- 15% dropout rate
- Overall alpha level = 0.05, two-tailed test
- Two planned comparisons

NICHD Reproductive Medicine Network
 PPCOS-Pregnancy in Polycystic Ovary Syndrome Protocol

1) Lowest rate vs. second lowest rate

2) Second lowest rate vs. highest rate

- χ^2 test for differences in proportions
- Best estimated live birth rates:
 - 1) Metformin alone: **30%**
 - 2) Clomiphene alone: **25%**
 - 3) Metformin + clomiphene citrate: **45%**

Parameters for sample size calculations:

- Alpha = **0.025**, two-tailed tests since two planned comparisons
- Beta = **0.20**, or 80% power

Sample Size

Treatment 1 (live birth rate)	Treatment 2 (live birth rate)	Required Sample Size	Sample Size with dropout adjustment	Total Sample Size

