The completed case report forms (CRF) will follow these guidelines: All data on the CRFs will be entered in ink. No data entry in the original CRF may be deleted or corrected by erasure, use of ink eradication fluid or any other such means. When a data entry is in error, draw a single line through the erroneous entry (the original data must remain discernible) and indicate the correct data in whatever way is appropriate. These changes should be initialed by the P.I. or designated study coordinator. Validity of data

NICHD Reproductive Medicine Network
PPCOS-Pregnancy in Polycystic Ovary Syndrome Protocol
recorded on CRFs during each patient visit will be attested to by one of the investigators
by a dated signature on an appropriate CRF page. All questions should be answered.
Data management will be as per DCC guidelines.

R. Competency to perform procedure/tests in the protocol

The principal investigator will be responsible for ensuring that laboratory and patient tests performed as part of the study are performed by competent personnel. These tests include semen analysis, ultrasonography of the pelvis, sonohysterography and/or hysterosalpingography of the uterus and fallopian tubes. The criteria for determination of competency may vary between sites in the study.

V. DATA ANALYSIS

All statistical tests will test non-directional hypotheses. The level of significance will be set at 0.05 for primary analyses and 0.05 for secondary analysis. An intent-to-treat principle will be employed during the primary analysis of the primary efficacy and safety measures. For the intent-to-treat analyses, randomized women will be included regardless of whether or not the patient received the assigned treatment, the patient was compliant with the treatment plan, and/or the treatment was administered according to randomization assignment.

A. Primary Efficacy Measure

Primary Analysis: A live birth will be defined as delivery of any viable infant. The primary analysis of the primary endpoint will include the following procedures. A chi-square test for equal proportions will be performed to evaluate whether live birth rate in Metformin/clomiphene group is the same as one in the group of either Metformin alone or clomiphene alone that has the higher live birth rate. If the test is not significant, a standard chi-square test will be used to examine differences in proportions in live births

NICHD Reproductive Medicine Network

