PPCOS-Pregnancy in Polycystic Ovary Syndrome Protocol
between the groups of Metformin alone and clomiphene alone. The level of significance for all tests included in the primary analysis will be 0.05.

Supplemental analyses: A set of secondary (supplemental/sensitivity) analyses of the primary endpoint will be conducted after the primary analysis has been performed using the intent-to-treat approach. All secondary analyses of the primary endpoint will be considered exploratory since the study has not been adequately powered for this set of supplemental analyses. Due to the exploratory nature of these analyses, the level of significance for the secondary analyses will be set at 0.05 (two-tailed) to reduce the Type II error rate.

Initially, a comparison of the internal consistency of live birth rates across sites will be examined using logistic regression analysis. Sites with similar live birth rates may be collapsed. For the regression model, the data will be examined to determine whether there is a site by treatment interaction effect. The recommended significance level is an alpha of 0.10 since the power to detect interactions is low. In the event that there is a significant interaction term, clinical site will be included as a covariate in all subsequent secondary analyses.

Next, logistic regression models will be used to evaluate the predictive value of treatment condition, clinical sites (if needed), prior exposure to either clomiphene citrate or metformin XR, and other explanatory factors on live birth rate. Examples of potential explanatory variables include: age, prior parity, body mass index, waist hip ratio, baseline proinsulin, insulin, and glucose values, and baseline testosterone values. In addition, we will examine to what extent change in baseline values is related to live birth rate.

Supplemental sensitivity analysis will also include an analysis of 'evaluable only' patients only (e.g., excluding randomized patients who were deemed to be ineligible later RMN Protocol
08Jan2004

NICHD Reproductive Medicine Network
PPCOS-Pregnancy in Polycystic Ovary Syndrome Protocol
or excluding patients who did not adhere to medication regimen) according to the
protocol).

B. Safety Measures

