- An ovulation will be defined as an elevated weekly progesterone level separated by at least one week with a nonovulatory progesterone level. A binary variable indication whether the patient ovulated or not will be created for each cycle. Furthermore, cycles to first ovulation will be used as time to event variable.
- Time to pregnancy is defined as the number of cycles required to achieve a viable implantation (detection of fetal heart beat). Weeks from pregnancy to live birth will also be used as a time to event variable for patients who did not have miscarriages.
- Conception. Conception is confirmed by a positive serum hCG value. Cycles to first conception will be used as a time to event variable.

E. Drop outs/Treatment Failures

Dropouts, either by patient choice or physician recommendation due to adverse effects or poor compliance will be analyzed by intention to treat as treatment failures. Subjects who have completed 30 weeks or 6 treatment cycles without a pregnancy will also be considered as treatment failures. Subjects who conceive and are lost to follow up will be considered as a treatment success. It is considered unlikely that the patients will be lost to follow-up after a conception on a treatment regimen.

NICHD Reproductive Medicine Network
PPCOS-Pregnancy in Polycystic Ovary Syndrome Protocol

F. Interim Analysis

Analysis Plan: An interim analysis will be conducted on the primary endpoint when 50% of the study participants have completed treatment. The primary analysis described above will be performed and the O'Brien-Fleming (1979) method will be applied to adjust for at the number of looks at the primary endpoint. The interim analysis should also provide a detailed summary of adverse events reported. The critical value for the primary analysis will be specified in the detailed analysis plan. The results of the interim analysis will be submitted to the Data Safety and Monitoring Committee (DSMC). The interim analysis results will be presented in a blinded fashion to the DSMC, who will then evaluate the findings to determine whether the trial should be continued, modified, or discontinued.

Stopping Rules: The stopping rule for the O'Brien-Fleming method compares the statistic Z_i with $Z^*(N/i)^{.5}$, where Z^* is the critical value for the significance level (.05), N is the total number of analyses ($N = 2$) and i is the analysis number (for the one planned analysis, $i = 1$).

VI. DISCLOSURE OF DATA

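### The O'Brien-Fleming stopping rule ties Z* to the .05 level and every primary test is set at 0.05; read as 1.960 at the final look, this gives a two-look error of about 5.2%, slightly above the stated 5%.

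*Protocol*

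**What the plan says.** All references are to the Protocol.

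- **Overall level.** Section IV.B.5 (Sample Size Calculations) lists "Overall alpha level = 0.05, two-tailed test". The opening of section V adds "All statistical tests will test non-directional hypotheses", so all critical values here are two-sided.
- **Level of the primary tests.** Section V.A (Primary Analysis) states: "The level of significance for all tests included in the primary analysis will be 0.05".
- **Interim look.** Section V.F states: "An interim analysis will be conducted on the primary endpoint when 50% of the study participants have completed treatment". The purpose of the adjustment is also given: the O'Brien-Fleming "method will be applied to adjust for at the number of looks at the primary endpoint".
- **Stopping rule.** Section V.F compares Z_i with Z*(N/i)^.5. It says that Z* "is the critical value for the significance level (.05") and that "N is the total number of analyses", set to 2. It spells out i = 1 for the one planned interim look.
- **Deferral.** Section V.F also says: "The critical value for the primary analysis will be specified in the detailed analysis plan". That plan is not available here.

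The protocol prints no numerical value for Z*, for the interim bound or for the final bound.

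**The concern.** The shape Z*(N/i)^.5 is the right one for O'Brien-Fleming. It holds the overall level only if the constant is solved for the planned number of looks. The single-look critical value is slightly too small for this purpose. It gives the whole 0.05 to the final look, and whatever is spent at the interim comes on top.

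Section V.F attaches Z* to the .05 level without mentioning the number of looks, and section V.A gives 0.05 as the level of every primary test. A reader who follows both sentences as they stand would use 1.960 in the formula and 1.960 at the end.

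What is at stake is narrow. A final p-value between 0.048 and 0.050 would be declared significant under that reading, but not under the two-look O'Brien-Fleming design that the section names. That case should be settled before any outcome data are seen.

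**Working it through.** **Inputs**

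- Overall two-sided alpha 0.05 (section IV.B.5; two-sided also from section V).
- N = 2 looks (section V.F).
- Information fraction at the interim 0.5. Section V.F sets the look at half of the participants completing treatment; treating that as half of the information is an assumption, varied below.
- Z* not printed. Two readings are compared: the single-look value 1.960, and the two-look constant.

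**Formula.** Under the null hypothesis, Z_1 and Z_2 for one comparison are bivariate normal with correlation sqrt(0.5). The overall two-sided error is

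P(|Z_1| ≥ c_1 or |Z_2| ≥ c_2) = 1 − P(|Z_1| < c_1 and |Z_2| < c_2),

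evaluated by numerical integration, with c_i = Z*·sqrt(2/i).

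**Reading A: Z* = 1.960, final test at 0.05**

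- c_1 = 1.960 × sqrt(2) = 2.772 (nominal p 0.0056).
- c_2 = 1.960 × sqrt(1) = 1.960 (nominal p 0.0500).
- Overall error = 0.0522. A simulation of 10 million draws gave 0.0521.

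**Reading B: Z* is the two-look constant.** Solving for overall error 0.05 gives Z* = 1.977.

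- c_1 = 2.797 (unrounded constant 1.97743 × 1.41421; nominal p 0.0052).
- c_2 = 1.977 (nominal p 0.0480).
- Overall error = 0.0500.

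**Mixed case: correct interim bound 2.797, final test left at 1.960.** Overall error = 0.0520. Most of the excess therefore comes from leaving the final test at 0.05, not from the interim bound.

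**Sensitivity of reading A to the information fraction**

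| Fraction | Overall error |
|---|---|
| 0.4 | 0.0528 |
| 0.5 | 0.0522 |
| 0.6 | 0.0515 |

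**At 0.025 per comparison**, the level used for sizing in section IV.B.5: the single-look value is 2.241 and the same construction gives 0.0256. The two-look constant is 2.250, with bounds 3.183 and 2.250 (nominal p 0.0015 and 0.0244), and gives 0.0250.

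**Cost in power.** For 45% against 30% with 197 per arm (the protocol's figures), use a fixed-sample normal approximation with unpooled variance:

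- SE = sqrt((0.45 × 0.55 + 0.30 × 0.70)/197) = 0.0482, so 0.15/SE = 3.113.
- Power at 1.960: Φ(3.113 − 1.960) = 87.5%.
- Power at 1.977: Φ(3.113 − 1.977) = 87.2%.

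**Scale in events.** With 226 per arm and a live birth rate of 30%, the standard error of the difference in counts is sqrt(2 × 226 × 0.3 × 0.7) = 9.74. Moving the final bound by 0.0175 shifts the required difference by 9.74 × 0.0175 = 0.17 of one live birth.

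**Discreteness.** Exact binomial error, with looks at 113 and 226 per arm and common rates of 20% to 45%, is 5.16% to 5.48% under reading A and 5.01% to 5.34% under reading B.

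**The case against.** The strongest reply is that the protocol does not fix reading A. Section V.F introduces the formula as the O'Brien-Fleming rule, gives adjustment for the number of looks as its purpose, prints no value and leaves the critical value to the analysis plan. In that setting, the critical value for level .05 can fairly mean the O'Brien-Fleming constant for an overall .05. The 0.05 in section V.A can likewise be the overall level before any sequential adjustment. Under those readings the formula gives 2.797 and 1.977, and the error is 5.0%.

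Much of this stands. A reader might infer that the trial's type I error does exceed 5% because of this rule. The documents do not support that: the value is deferred, and the charitable reading is open.

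The deferral does not remove the point, though. The protocol goes beyond leaving a number blank. It defines Z* by the .05 level and sets all primary tests at 0.05. A plan that uses 1.977 at both looks would test at 0.0480 at the end, which does not match section V.A as worded. If only Z* is read charitably and section V.A is followed as it stands, the error is still 5.20%.

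The objection that the effect is tiny also stands. It is 0.2 percentage points, a fraction of one live birth at the final bound. The discreteness of the chi-square test is of similar size, and the corrected bounds do not give exactly 5% either. That limits the importance of the point but does not make the wording right.

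A reader might also add this excess to the conflict between 0.025 per comparison in section IV.B.5 and 0.05 in section V.A. That is a separate matter. The figures here cover two looks at one comparison only.

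**Conclusion.** The point holds as a minor wording error. If Z* is taken as 1.960 and the final test stays at 0.05, the bounds are 2.772 and 1.960 and the two-sided error for one comparison is about 5.2%, against the stated 5%. If the analysis plan uses 1.977 at both looks, the excess does not arise, but section V.A would need rewording to agree with it.

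The 5.2% rests on the normal approximation, half of the information at the interim, and a single comparison. It leaves out the second primary comparison and the choice of the better single-agent arm. Over information fractions of 0.4 to 0.6 the figure stays between 5.15% and 5.28%.

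**What to change.** - **Section V.F.** Define Z* as the two-look O'Brien-Fleming constant for the chosen alpha, and print both bounds. For 0.05: Z* = 1.977, bounds 2.797 and 1.977. For 0.025 per comparison: Z* = 2.250, bounds 3.183 and 2.250.
- **Section V.A.** State that 0.05 is the overall level and that the final test uses the reduced nominal level: 0.0480, or 0.0244 if 0.025 per comparison is used.
- **Analysis plan.** Carry the same constants, so that the two documents agree.

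The cost is a sentence in each place and about 0.3 percentage points of power at the design rates. The sample size need not change. Which alpha applies per comparison has to be settled separately; the constants above cover either choice.

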Event	Baseline	Weekly Visit	Monthly Visit	Study Drug Termination	Pregnancy Visit	Pregnancy Outcome
Obtain consent						
Complete Physical						
Ultrasound						
Safety labs blood work						
Metabolic/ Reproductive Blood work						
Progesterone Level						
Appropriate CRFs						
Other Procedures	Semen-analysis, tubal patency test		Dispense medication, obtain WT and WHR			

NICHD Reproductive Medicine Network
PPCOS-Pregnancy in Polycystic Ovary Syndrome Protocol

APPENDIX B: Risk Factors for Genetic Disorder

- 1) Will you be age 35 or older when your baby is due? _ Yes_ No
- 2) If you or your partner is of Mediterranean or Asian decent, do either of you or anyone in your families has thalassemia? _ Yes_ No
- 3) Is there a family history of congenital heart defects? _ Yes_ No
- 4) Is there a family history of Down syndrome? _ Yes_ No
- 5) Have you ever had a child with Down syndrome? _ Yes_ No
- 6) If you or your partner is of eastern European Jewish or French Canadian descent, is there a family history of Tay–Sachs disease? _ Yes_ No
- 7) If you or your partner are of eastern European Jewish descent, is there a family history of Canavan disease? _Yes_ No
- 8) If you or your partner is African American, is there a family history of sickle cell disease or trait? _Yes_ No
- 9) Is there a family history of hemophilia? _Yes_ No
- 10) Is there a family history of muscular dystrophy? _ Yes_ No
- 11) Is there a family history of cystic fibrosis? _ Yes_ No
- 12) Is there a family history of Huntington disease? _Yes_ No
- 13) Is anyone in your or your partner's family mentally retarded? _ Yes_ No
- 14) If so, was that person tested for fragile X syndrome? _ Yes_ No
- 15) Do you, your partner, anyone in your families, or any of your children have any other genetic diseases, chromosomal disorders, or birth defects? _ Yes_ No
- 16) Do you have a metabolic disorder such as diabetes or phenylketonuria? _ Yes_ No
- 17) Have you had more than two miscarriages in a row? _Yes_ No
- 18) Have you ever had a baby who was stillborn? _ Yes_ No
- 19) Is there a family history of alpha-1 antitrypsin deficiency? _ Yes_ No

NICHD Reproductive Medicine Network
 PPCOS-Pregnancy in Polycystic Ovary Syndrome Protocol

Appendix C: Core Lab Instructions from UVA Center for Research in Reproduction

[contact] [contact] EMAIL: [contact]

ASSAY	TOTAL TESTOSTERONE	SHBG	INSULIN	PROINSULIN	GLUCOSE
METHOD	IMMULITE	IMMULITE	IMMULITE	ELISA	OLYMPUS
SAMPLE TYPE	SERUM	SERUM	SERUM/ HEP. PLASMA	SERUM	SERUM
SAMPLE VOLUME	20 UL X2	10 UL X2	100 UL X2	50 UL X2	50 UL X2
MIN. DEAD VOLUME	100 UL	100 UL	250 UL	NA	NA

NA= NOT APPLICABLE

MINIMUM TOTAL SAMPLE VOLUME NEEDED TO ASSAY ALL TESTS = 2 ML OF SERUM

SAMPLE COLLECTION PROCEDURES:

Normal venipuncture procedures should be followed. Please collect enough blood in a red top tube to give you a minimum of 2 ml of serum. Allow red top to clot 15- 30 minutes before separating. Separate by centrifuging samples 10 minutes at 4°C or room temperature and 3000 RPMs. Aliquot serum samples into two plastic screw cap 1.5 ml vials with O-rings. Aliquots may be temporarily maintained at -20°C in a non frost-free freezer, but should be moved to a -70°C or -80°C freezer as soon as possible.

SHIPPING INSTRUCTIONS:

1. Notify lab before shipping samples. (Do not ship for weekend delivery.)
2. Ship samples frozen in watertight receptacles on dry ice by Fed-Ex Priority Overnight. Please adhere to all rules regarding shipment of hazardous material from your institution.
3. Ship to the following address: **University of Virginia
 Center for Research in Reproduction
 [name]
 [name]
 Attn: [name], MT**

NICHD Reproductive Medicine Network
PPCOS-Pregnancy in Polycystic Ovary Syndrome Protocol

SAMPLE LABELING:

Each sample is to be identified with one of the provided labels. The patient's assigned randomization number, visit number and date specimen obtained are to be entered on the label. Each core lab shipment must be accompanied by the UVA Core Lab Shipment Form.

DATA OUTPUT:

The data will be transferred to the DCC and emailed to the appropriate investigator at the completion of the study as an Excel document, which will include the following information:

- Sample #**
- History #**
- Average Result**
- Mean**
- SD**
- CV%**

Core Lab Blood Draw Schedule

*All blood draws are fasting

Baseline	Monthly Visit	Study Drug Termination Visit

 ▪ 7.5cc red top to be drawn fasting within 30 days prior to randomization (recommend drawing red top the same time as safety labs) 	
 ▪ 7.5cc red top drawn fasting at each monthly visit 	
 ▪ 7.5cc red top drawn fasting

 ▪ Centrifuge for 10 minutes at 3000 RPM 	
 ▪ Centrifuge for 10 minutes at 3000 RPM 	
 ▪ Centrifuge for 10 minutes at 3000 RPM

 ▪ Aliquots Fill two 1.5ml vials with serum for core lab 
Dispense remaining serum into 0.5ml aliquots. Maintain at site for future research.
	
 ▪ Aliquots Fill two 1.5ml vials with serum for core lab 
Remaining serum to be placed into 1 vial and maintained at site.
	
 ▪ Aliquots Fill two 1.5ml vials with serum for core lab 
Remaining serum to be placed into 1 vial and maintained at site.

NICHD Reproductive Medicine Network
PPCOS-Pregnancy in Polycystic Ovary Syndrome Protocol

Appendix D: List of common medications excluded or requiring wash-out period.

PPCOS Excluded Medications

A patient will be excluded from study if they are taking any medication that should not be discontinued and this medication would affect reproductive function or metabolism, or would interact with either study medication.

Angiotensin Converting Enzyme (ACE) Inhibitors

Prinivil (lisinopril)
Captoten (captopril)
Cozaar (losartan)
multiple others

Antidysrhythmics

Procainamide (Pronestyl)
Digoxin (Lanoxin)

Antimalarial

Quinine

Calcium Channel Blockers

diltiazem (Cardizem, Dilacor, Tiazac, Diltia-XL)
verapamil (Isoptin, Calan)
amlodipine (Norvase)
felodipine (Plendil)
isradipine (DynaCirc)
nicardipine (Cardene)
nifedipine (Procardia, Adalat)
nifsoldipine (Sular)

Somatostatin

octreotide (Sandostatin)
lanreotide

Diuretics

Amiloride (Midamor)
Furosemide (Lasix)
Triamterene (Dyrenium)

Steroids

Prednisone (Deltasone)
Dexamethasone (Decadron)

A short course of steroid therapy for treatment of asthma will not qualify as a reason to withdraw a patient from the study.

Vasodilator

Diazoxide

Hormonal Medications Requiring 1 month wash-out:

Progestins (Oral or Cyclic)

medroxyprogesterone acetate (Provera, Cycrin, Amen, Curretab)
megestrol (Megase)
norethindrone (Aygestin)
progesterone gel (Crinone)
Micronized progesterone (Prometrium)

GnRH Agonists/Antagonists

Leuprolide (Lupron)
nafarelin (Synarel)
buserelin
gosarelin (Zoladex)
ganarelix (Antagon)
cetorelix (Cetrotide)

Gonadatropins

Pergonal
Repronex
Follistim
Gonal-F
Fertinex
Metrodin

Other medications Requiring 1 month wash-out:

Anti-androgens

cyproterone (Cyprostat)
spironolactone (Aldactone)
flutamide (Eulexin)
finasteride (Proscar, Propecia)

Anti-obesity

diazoxide (Proglycem)
orlistat (Xenical)
sibutramine (Meridia)
diethylpropion (Tenuate)
phendimetrazine (Bontril)
phentermine (Adipex-P, Fastin, Ionamin)

Hormonal Medications Requiring 3 month Wash-Out Period:

Clomiphene citrate (Clomid, Serophene)

Depot GnRH agonists

Injectable Contraceptives

medroxyprogesterone acetate (Depo Provera)

Oral Contraceptives

Any Brand

Progestins (Not including cyclic)

Any Brand

Other Medications Requiring 3 month Wash-out Period:

Anti-Acne

isotretinoin (Accutane)

Anti-diabetic

acarbose (Precose)

Insulin

sulfonylureas

acetahexamide (Dymelor)

chlorpropamide (Diabinese)

tolazamide (Tolinase)

tolbutamide (Orinase)

glimepiride (Amaryl)

glipizide (Glucotrol)

rosiglitazone (Avandia)

pioglitazone (Actos)

Biguanides

metformin (Glucophage)

Medications with potential longer washouts (Contact DCC)

Contraceptive Implants

Norplant (levonorgestrel implants)

